6.1 Inclusion and exclusion criteria

Based on the current version of the SmPC for anastrozole patients participating in this study must meet all of the following criteria:

1. Provision of Written Informed Consent
2. Postmenopausal women aged 18 years or older;
Postmenopause is defined as
 - Natural menopause with menses >1 year ago or
 - Serum FSH (> 20 IU/ l), and E2 levels in the postmenopausal range or
 - patients who had bilateral oophrectomy
3. Histologically / cytologically confirmed primary diagnosis of early breast cancer (M0) with hormone sensitive tumour (ER+ve and/or PgR+ve)
4. Patients, who underwent breast cancer surgery and, if applicable, radiation therapy and/ or neo/adjuvant chemotherapy and have taken adjuvant endocrine treatment with anastrozole (upfront or following two to three years of tamoxifen treatment) for at least 3 month and for a maximum of 6 months
5. Patient is considered suitable for treatment with an oral therapy.
6. Ability to organize the daily intake of drugs
7. Ability to read and understand German

8. In case of a previous therapy with tamoxifen (switch-therapy), duration of tamoxifen treatment for at least two and up to three years.

Any of the following is regarded as a criterion for exclusion from the program:

1. Patients, who are unable to provide written consent
2. Concomitant treatment with drugs known to affect sex hormonal status and Tamoxifen
3. Known hypersensitivity to anastrozole or any excipients of the tablet. The contraindications, warning notices and measures of precaution of this product, as notified in the product information, have to be respected
2. Patients with ductal carcinoma in situ (DCIS) without primary diagnosis of early breast cancer (M0)
3. Evidence of any significant clinical disorder or laboratory finding which in the opinion of the investigator, makes it undesirable for the patient to participate in the program
4. Previous enrolment in the present program
5. Participation in any other clinical trial within 30 days of enrolment
8. Involvement in the planning and conduct of the program (applies to both AstraZeneca staff or staff at a participating site or at the CRO).

7. PROGRAM PLAN AND PROCEDURES

7.1 Overall design and flow chart

This is an open, multicentre NIS.

[figure not shown]
It is planned to enrol subjects into this NIS between Q1 2009 and Q1 2010. Based on the plan outlined below, it is assumed that the last subject will be enrolled in Q1 2010 and subsequently documented until Q4 2010.

The treatment with anastrozole can be stopped at any time.

Furthermore it is expected, that the last completed eCRF will be filled in Q4 2010. It is planned to close all centres until end of Q1 2011 (i.e. the fees for all participating centres are paid).

Treatment with Anastrozole

Study duration

*or at point of treatment discontinuation

Evaluation period

Information to patients: study start, weeks 1, 3, 5, 8, 12, 20

- 1 The start of the adjuvant treatment with anastrozole is defined by the date of the first tablet intake. If this date is not available, the date of first prescription will be taken.
- 2 The end of participation in this NIS is defined as recurrence or death or withdrawal of informed consent is documented via WBDC. Patients who stop endocrine therapy (i.e. do not take further treatment) or patients who switch to an adjuvant endocrine therapy with tamoxifen or a different aromatase inhibitor or patients considered 'lost to follow-up' (i.e.: can no longer be contacted) will be documented as premature terminations. Otherwise this NIS terminates after completion of 12 (15) months observation period (12 respectively 15 months observation period results from time slot for inclusion, minimum 3 and maximum 6 months of anastrozole therapy prior to enrolment)

7.2 Program plan

	3 – 6 months before study start	Study start	3, 6, and 9 months after study start
Start of adjuvant treatment with anastrozole (upfront or switch following tamoxifen treatment)	X		
Written Informed consent		X ¹	
Registration inclusion/exclusion criteria (online eCRF)		X	
Activation of the further online documentation forms		X ²	
Baseline documentation (online eCRF; see chapter 8)		X	
Follow-up documentation (online eCRF; see chapter 8)			X
Entrance-Questions eCRF (status activates applicable modules)			X
AE/SAE – module (eCRF)		X	X ^{3,4}
Therapy continuation module (eCRF)			X ³
Therapy discontinuation module (eCRF)			X ^{3,5}
Recurrence module (eCRF)			X ^{3,5}
Death module (eCRF)			X ^{3,5}
Consent withdrawn module (eCRF)			X ^{3,5}
Treatment change module (eCRF)			X ^{3,5}
Patient’s questionnaires		X ⁶	X ⁷

¹ Patient’s written Informed Consent must be obtained before registration of the patient for the program, for details please see Section 7.3. A copy of the Patient information and Informed Consent Form can be found in Appendix B.

² Activation of the further online documentation forms will take place within a few hours after online registration on the same day during normal office working time (9 – 16 h). If the online registration was performed in the evening, on a weekend or a holiday, activation of the further online documentation forms will take place on the next working day. For details please see Section 7.4.

³ Completion if applicable. The e-documentation at 3, 6, and 9 months starts with entrance questions concerning patient’s status. These questions activate other relevant documentation-modules.

⁴ SAE must be reported to AstraZeneca drug safety within 1 day of notification, for details concerning SAE please see Sections 8.3 and 8.3.1.3.

⁵ Recurrence, death, withdrawal of consent, treatment discontinuation and switch to an adjuvant endocrine treatment with tamoxifen or a different aromatase inhibitor must be documented immediately. If one of these events is documented the sending of patient material will be stopped.

⁶ Patient’s questionnaires “Start”.

Observation Plan
Drug Substance Anastrozole
Code NIS-ODE-ARI-2008/1
Date 19 Mar 2009 (Version 1.4)

⁷ Patient's questionnaires "Follow up".

7.3 Informed consent and patient data

The investigator(s) at each clinic will ensure that the patient is given full and adequate oral and written information about the nature and purpose of the NIS as well as the use of patient's data and storage of patient's names and addresses during the program. The patients must also be notified that they are free to discontinue from the program at any time. The patient should be given the opportunity to ask questions and allowed time to consider the information provided.

The patient's informed consent contains the full name of the patient and her address and the name of the investigator. The informed consent form must be signed and dated by the patient and the investigator. The patient's signed and dated informed consent as well as investigators signature must be obtained before registration. The investigator(s) at the clinic or the office based physician must store the original, signed Informed Consent Form according to legal requirements. A second original copy of the signed Informed Consent Form must be given to the patient. A copy of the patient's information consent form can be found in Appendix B.

A copy of the completed and signed patient's informed consent must be sent by fax to . The informed consent will be stored by until the end of the NIS (final analysis completed). After completion of the program all Informed Consent Forms will be destroyed by . The destruction must be documented and confirmed in written form.

Patient names and addresses are required for the shipment of information material to patients. Furthermore, upon consent by the patients, may contact the patients per mail in case the patient questionnaire was not received by (at maximum, one written contact per patient documentation will be allowed).

For the handling of patient names and addresses a separate database will be used, as well as for the information obtained by the sick fund. This database will be operated within the facilities of only. The patients' address database will be linked through the registration number with the study database. Links to other databases will not be implemented. At the end of the NIS (final analysis completed) all patient names and addresses must be deleted from this database. The deletion must be confirmed in written form.

The sponsor of this NIS has no access to patient names and addresses.

Patients, who are insured by a sick fund organized by "Gesellschaft für Wirtschaftlichkeit und Qualität bei Krankenkassen" (GWQ) are asked to take part for special settlement informations by their sick fund. For this information it is necessary to get the sick fund and the insurance policy number. In addition to the informed consent for the main COMPACT program (Appendix B-1), an additional informed consent form will be signed (Appendix B-2). Patients will be informed that the participation at the special settlement is not mandatory for the participation at the COMPACT program. Patients who sign the additional Informed Consent Form agree that their sick fund data about breast-cancer related costs and arthralgia therapy will be combined with the study datasets by a third party using the patient

sick fund and insurance number which will be sent to _____ on the additional informed consent (Appendix B-2). Patients agree that data transferred from the sick funds will concern data from 12 months before study start up to the end of the study for the respective patient. The patient insurance number will be immediately deleted after data combination.

A copy of the completed and signed additional patient's informed consent must be sent by fax even to _____. The informed consent will be stored by _____ until the end of the NIS (final analysis completed). After completion of the program all Informed Consent Forms will be destroyed by _____.

7.4 Registration of patients

Patients meeting all eligibility criteria and having given written informed consent (Appendix B) will be enrolled by the site using an online registration form. Registration will be possible 24 hours a day via the COMPACT-webpage: www.compact-programm.de

Registration

For the registration of a patient

- a copy of the signed informed consent form must be faxed to _____, to

and

- the registration form must be completed online via the COMPACT-webpage: www.compact-programm.de

If patients take part in the additional information program from the sick fund

- a copy of the signed additional informed consent form must be faxed to

7.5 Information

Patients will undergo standard routine care for breast cancer. Additionally, information will be provided to patients by mail. The information material includes patient support materials (letters and brochures) with general background information on breast cancer, coping with the diagnosis, lifestyle and diet. Additionally patient questionnaires will be sent at the start of the study and 3, 6 and 9 months after study start. Table 1 provides an overview of the topics of the patient support materials, questionnaires and the timing of the mailings. The information packages will be sent to the patients at the indicated time points after the registration of the patient.

Table 1 Patient materials packages, mailing frequency and themes

Time point of mailing	Patient's material
Week 0	
Letter: "Die Antihormontherapie – Ihr starker Begleiter" („Antihormone therapy - your strong companion“)
 
Brochure 1 „Alle Chancen nutzen“ („Taking all chances“)

Week 1	
Brochure 2 "Was Sie über Nebenwirkungen des Aromatasehemmers wissen sollten" („What you should know about side effects of aromatase inhibitors“)

Week 3	
Letter: "Was hilft, wer hilft - Partner und Verbündete" („What helps, who helps – partner and leagues“)
 
Brochure 3 „Was Sie über Kommunikation wissen sollten“ („What you should know about communication“)

Week 5	
Brochure 4 "Was Sie über Fatigue-Syndrom und Lymphödem wissen sollten" („What you should know about Fatigue Syndrome and Lymphedema“)

Week 8	
Letter: "Bewusstes Leben - der eigene Körper" („Conscious life – your own body“)
 
Brochure 5 „Was Sie über Umgang mit Ängsten wissen sollten“ („Dealing with anxieties, what you should know“)

Week 12 (month 3)	
Brochure 6 "Was Sie über Brustkrebs und Sexualität wissen sollten" („What you should know about breast cancer and sexuality“)

Week 20	
Letter: "Kraft & Lebensenergie - der Blick nach vorn" („Power & Vitality – looking ahead“)
 
Brochure 7 „Was Sie über regelmäßige Bewegung und den Umgang mit Ängsten wissen sollten“ („Regular exercise and dealing with anxieties, what you should know“)

Mailing of the patient materials will be stopped:

- if breast cancer recurrence or patient's death is documented by the investigator via WBDC
- or if stop of adjuvant endocrine treatment (no further continuation of adjuvant treatment at all) or switch to a different adjuvant endocrine treatment with tamoxifen or a different aromatase inhibitor is documented by the investigator via WBDC
- or if patient withdraws consent (documented by the investigator via WBDC)
- or if _____ is notified either by physician or by patient that the patient does not wish to receive further mailings.

Patient materials will be sent to the patients by mail. The mailing of the appropriate patient material packages at the appropriate time points will be coordinated and organised by _____.

7.6 Discontinuation of patients from program

Patients may discontinue participation in this program at any time. Specific reasons for discontinuing a patient from this program are:

- Withdrawal of informed consent
- Breast cancer recurrence
- Stop of adjuvant endocrine treatment (no further continuation of adjuvant treatment at all) or switch to an adjuvant endocrine treatment with tamoxifen or a different aromatase inhibitor

Patients should always be asked about the reason(s) for their discontinuation and the presence of any adverse events. For these cases, the investigator has to complete the consent withdrawal form and the respective forms in the eCRFs.

7.7 Concomitant treatment(s)

Any medication, which is considered necessary for the patient's safety and well-being, may be given at the discretion of the investigator(s). However possible drug interactions as specified in the current SmPC should be taken into account. A copy of the current SmPC for anastrozole can be found in Appendix C.

8. DOCUMENTATION

8.1 Patient documentation by investigator

The following data will be collected via web based data capture (WBDC) by the investigator or a designated delegate.

8.1.1 Documentation at registration

The following data should be documented at registration/enrolment

Demographics	Year of birth
Patient number	
Patient insured in a sick fund part of GWQ?	Yes; no
Informed consent	
Inclusion / exclusion criteria	
Was the patient identified for anastrozole therapy 1mg / day?	Yes; no
Date of the 1 st prescription	
Start date of anastrozole therapy	
Breast centre that performed surgery	Name Address
Investigator details	Fax number E-mail address Name

8.1.2 Documentation at baseline

The following data should be documented at baseline:

Demographics	Height (cm) Weight (kg) BMI
Menopausal status	
Age of patient when entering menopause	
Did the patients receive any hormone replacement therapy before?	Yes, no; if yes => duration of hormone replacement therapy?
Specification of hormone replacement therapy	Estrogen only (dose of estrogen); Estrogen-gestagen combination (dose of estrogen)
Concomitant diseases	Answers for each listed point (no, yes – please specify, unknown) Cardio-circulatory system

	
vascularly system skeleton, musculature (i.e. rheumatoid arthritis, arthralgias, osteoarthritis, back pain, capral tunnel syndrome; soft tissue rheumatism; other musculature and joint discomfort) if arthralgias occurred => pre-existing arthralgias before anastrozole therapy? => if yes: intensity? localisation? duration?; => any arthralgia occurrence after the start of anastrozole therapy? if yes => Arthralgia AE module
 
Urogenital system Central nervous system Gastrointestinal system Metabolic diseases Hot flushes Headache / migraine Other

Primary diagnosis of breast cancer	Date of primary diagnosis
Number of tablets currently taken by patient per day	
Localisation of primary tumour	
Anastrozole indication	Upfront or following tamoxifen treatment if following tamoxifen treatment: duration of tamoxifen therapy
Breast cancer therapies	Performance of post-operative radiation therapy (no, yes) Performance of neo-adjuvant chemotherapy (CHT) (no, yes; number of cycles) Performance post-operative chemotherapy (no, yes; number of cycles)
Treatment compliance: doctor`s assessment	Estimation of compliance by doctor`s judgement: “How many tables have been taken in the observed period?” (none, few, less than half, appr. half, more than half, almost all, all)
Concomitant medication	No, yes => please specify

Arthralgia – Module (to be filled in in case of arthralgia occurrence during anastrozole therapy)	
Arthralgia questionnaire	
Arthralgia onset during anastrozole therapy (no, yes, unknown – if yes : localisation, swelling, pain intensity; duration, relationship to study drug) Therapy of arthralgias: no, yes – please specify.
 
Assessment of treatment with medication (drug name, dose, package size, duration (start-end))
 
Doctor`s visits (including doctor`s specification)
 
Diagnostics? if yes => specify
 
Physiotherapy? if yes => specify
 
Adjuvants? if yes => specify
 
Lifestyle changes? if yes => specify

8.1.3 Documentation after 3, 6, and 9 months after study start

The following patient data should be documented after 3, 6, and 9 months after study start or at the time point of treatment discontinuation:

Observation interval	Date of last examination Date of documentation (current date)
Date of observation	
Patient lost to follow-up status	If the patient does not attend follow-up visits, can she be contacted (yes, no – lost to follow-up)
Demographics	Weight (kg)
Occurrence of adverse events	(no, yes) ⇒ AE/SAE-module
Status of breast cancer disease	Loco-regional recurrence / contralateral recurrence / distant metastasis (if yes: date of recurrence / localisation?)
Survival status	(alive, died) ⇒ Survival –module
Continuation of anastrozole therapy (yes, no)	Yes ⇒ Treatment continuation-module No ⇒ Treatment discontinuation module Change of endocrine therapy ⇒ Switch module
Patient continuation of participation in COMPACT	(Yes, no – consent withdrawn, no – died, no – other reasons) ⇒ Consent withdrawal-module
Concomitant medication	No, yes => please specify

The following data should be documented after 3, 6, and 9 months of endocrine therapy or at the time point of treatment discontinuation as indicated and applicable by patient's status:

Treatment continuation – Module (continuation of anastrozole therapy)	
Treatment compliance: doctor's assessment	Estimation of compliance by doctor's judgement: "How many tables have been taken in the observed period?" (none, few, less than half, appr. half, more than half, almost all, all)
Number of medicines / tablets or capsules per day	
Anastrozole prescriptions / sample packages	Number and package size
Was anastrozole intake stopped / taken irregularly?	if yes => reason?
Concomitant medication	No, yes => please specify

Arthralgia – Module (to be filled in in case of arthralgia occurrence during anastrozole therapy)	
Arthralgia questionnaire	
Arthralgia onset during anastrozole therapy (no, yes, unknown – if yes : localisation, swelling, pain intensity; duration, relationship to study drug)
 
Therapy of arthralgias: no, yes – please specify.
 
Assessment of treatment with medication (drug name, dose, package size, duration (start-end))
 
Doctor's visits (including doctor's specification)
 
Diagnostics? if yes => specify
 
Physiotherapy? if yes => specify
 
Adjuvants? if yes => specify
 
Lifestyle changes? if yes => specify

Treatment discontinuation – Module (discontinuation of anastrozole therapy)	
Treatment compliance: doctor's assessment	Estimation of compliance by doctor's judgement: "How many tables have been taken in the observed period?" (none, few, less than half, appr. half, more than half, almost all, all)
Questions on arthralgias and	assessment of arthralgia occurrence during therapy with

related costs	
anastrozole (no, yes, unknown - if yes : localisation, swelling, pain intensity: mild/moderate/severe; duration, relationship to study drug: certain, probable, possible, unlikely, not related; serious: yes/no) Therapy of arthralgias: no, yes – please specify.
 
Assessment of treatment with medication (drug name, dose, package size, duration (start-end))
 
Action in concern of the therapy with anastrozol
 
Outcome
 
Relationship to anastrozole therapy, and treatment with medication
 
A reason to discontinue the therapy with anastrozol? SAE?

Discontinuation of treatment with anastrozole	
Date of last intake, unknown
 
Reasons for discontinuation (recurrence, death, patient's wish, physician's recommendation and specification of reasons, other, interactions with concomitant medication, AE – worsening of a concomitant disease: (hot flushes, headache, joint pain/arthritis complains (fingers, hands, arm, shoulder/ feet, knees, hip / spine), other)
 
AE – new: (hot flushes, headache, joint pain/arthritis complains (fingers, hands, arm, shoulder/ feet, knees, hip / spine), other)

Continuation of other endocrine treatment	
(no)
 
(yes – change of endocrine therapy which drug: tamoxifen, letrozole, exemestane, other - specification)

Switch – Module (continuation of endocrine therapy with tamoxifen or a different aromatase inhibitor)	
Continuation of other endocrine treatment	
(no)
 
(yes – change of endocrine therapy which drug: tamoxifen, letrozole, exemestane, other - specification)

Discontinuation of treatment	
Date of last intake, unknown
 
Reasons for discontinuation (recurrence, death, patient's wish, physician's recommendation and specification of reasons, other, interactions with concomitant medication, AE – worsening of a concomitant disease: (hot flushes,

	headache, joint pain/arthritis complains (fingers, hands, arm, shoulder/ feet, knees, hip / spine), other) AE – new: (hot flushes, headache, joint pain/arthritis complains (fingers, hands, arm, shoulder/ feet, knees, hip / spine), other)
--	--

Death - Module	
	Date of death Reason of death (due to tumour and complications and progression, due to tumour and adverse event, not due to tumour, dependency to tumour not evaluable) Reason of death unknown, specification possible

Consent withdrawal - Module	
	Date consent withdrawn Reason for consent withdrawn (friends, family advise not to participate, patient refusal to complete questionnaires, patient rejection of information material, patient no longer wishes to support research, unknown, other) Patient agreement to complete a final questionnaire (no/yes)

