11.3 Description of analysis sets

The following analysis data sets will be used in the statistical analysis:

Safety population:

This population will consist of all patients enrolled at Visit 1 into this NIS who have taken at least one anastrozole tablet (with a documented date of 1st intake of anastrozole; if unavailable, date of 1st prescription of anastrozole may be used).

Intention-to-Treat (ITT) population:

This population will consist of all documented patients from the safety population for whom – based on CRF documentation - a determination of their compliance and/or incidence of arthralgias within the first 3 months after study start is possible.

Other analysis sets may be defined. Details about the definition of these additional analysis sets will be given in the SAP.

The ITT analysis set will be used for the primary analysis of compliance and arthralgias. The safety population will be the basis for the safety analyses and an additional secondary analysis of arthralgias.

Demographic data and all other important baseline characteristics will be presented for both, the ITT and safety analysis sets. The results will be presented in a descriptive way.

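### At 3, 6 and 9 months the eCRF has no named, unconditional arthralgia question for women who continue anastrozole, so doctor-recorded arthralgia is ascertained differently by treatment status

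*Protocol*

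**What the plan says.** Protocol section 7.2 (footnote 3) says the follow-up forms begin with entrance questions on the patient's status: "These questions activate other relevant documentation-modules". Section 8.1.3 lists what is then documented.

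- **Every woman:** a general adverse-event item, "no, yes) ⇒ AE/SAE-module", with disease status, survival, continuation of anastrozole, participation and concomitant medication. None of these names arthralgia.
- **Women who continue:** "Yes ⇒ Treatment continuation-module". That module covers the doctor's compliance rating, tablet counts, prescriptions, irregular intake and concomitant medication. It has no arthralgia item.
- **Arthralgia module:** "Arthralgia – Module (to be filled in in case of arthralgia occurrence during anastrozole therapy". Its first item is "Arthralgia onset during anastrozole therapy (no, yes, unknown".
- **Women who discontinue:** the Treatment discontinuation module has a fixed row, "assessment of arthralgia occurrence during therapy with" anastrozole, also answered no, yes or unknown.
- **Women who change endocrine therapy:** the Switch module mentions joint pain only as a possible reason for stopping.

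The baseline form (section 8.1.2) names arthralgia among the skeletal conditions and asks about "any arthralgia occurrence after the start of anastrozole therapy", with a yes leading to the module. The patient questionnaire (section 8.2.2) asks directly about arthralgia in the preceding three months and carries the VAS. It is due at 3, 6 and 9 months or when treatment is stopped. Section 11.3 admits a patient to the ITT population if, on CRF documentation, "a determination of their compliance and/or incidence of arthralgias within the first 3 months after study start is possible".

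**The concern.** How likely a doctor is to record arthralgia depends partly on whether the form asks about it. Here the prompt differs with the woman's treatment status: a fixed question if she discontinues, a general adverse-event item and a conditional module if she continues, and only a reason-for-stopping list if she is routed to the Switch module. A difference in recorded arthralgia between these groups could then come from the form rather than from the patients.

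Section 11.4.1 plans several secondary analyses that may draw on the eCRF: incidence by interval, time to first arthralgia, relationship to study drug, and factor models for arthralgia and for compliance. A later SAP can choose how to handle blanks, but it cannot recover an answer that was not collected.

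**Working it through.** The plan gives no figure to reproduce. The check is a comparison of routes, followed by an illustration of scale.

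**Step 1. The routes side by side**

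| Form | Arthralgia on the eCRF | Named and put to every woman on that route? |
|---|---|---|
| Baseline (8.1.2) | Named condition, explicit question opens the module | Yes |
| Follow-up, continues (8.1.3) | General adverse-event item; module if arthralgia has occurred | No |
| Follow-up, discontinues (8.1.3) | Fixed row: no / yes / unknown | Yes |
| Follow-up, changes therapy (8.1.3) | Joint pain only as a reason for stopping | No |

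The discontinuation module also has a row on continuing with another endocrine treatment, so it is unclear whether women who change therapy complete both modules.

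**Step 2. What a blank means.** For a continuer, an empty Arthralgia module fits three situations: no arthralgia, arthralgia not asked about, or module not completed. If blanks are read as 'no', incidence in continuers can be too low. If they are read as missing, the continuers with arthralgia information are mainly those who have arthralgia, and incidence is too high.

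**Step 3. The ITT rule.** Section 11.2 calls a patient compliant only if doctor and patient both score 5 or 6. If the doctor scores 5 or 6 and no questionnaire comes back, that definition cannot be settled. Entry to the ITT set may then turn on the arthralgia limb, where Step 2 applies. How often this happens cannot be derived from the protocol. It would be rare if the doctor's rating alone counts as a determination of compliance.

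**Step 4. Illustration of scale**

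Inputs:
- True rate p = 0.356 in both groups. This is the joint-disorder rate on anastrozole that section 1.1 cites from a randomised trial, where 68 months' median follow-up is given. It is used for scale only.
- Recording when asked directly r₁ = 0.95, and when not asked r₀ = 0.50 to 0.90. Both are assumptions; the protocol gives no recording rates.

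Observed rate = p × r. Spurious odds ratio = [p r₁ / (1 − p r₁)] ÷ [p r₀ / (1 − p r₀)].

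Stoppers: 0.356 × 0.95 = 0.338, odds 0.338 / 0.662 = 0.511.

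| r₀ | Observed in continuers | Odds | Odds ratio |
|---|---|---|---|
| 0.50 | 0.178 | 0.217 | 2.36 |
| 0.60 | 0.214 | 0.272 | 1.88 |
| 0.75 | 0.267 | 0.364 | 1.40 |
| 0.90 | 0.320 | 0.471 | 1.08 |
| 0.95 | 0.338 | 0.511 | 1.00 |

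The last row is the case of equal recording, in which the artefact disappears.

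**The case against.** The strongest reply is that section 8.1.3 lists data to be documented and is not a screen-by-screen flow. The general adverse-event item goes to every woman, and section 8.1.2 calls the form the Arthralgia AE module, so that item may be the intended trigger. Doctors are briefed on the objectives (section 9) in a study about arthralgia, so near-complete recording is plausible. This stands as far as it goes: cases can be captured, and the loss may be small. But the adverse-event item does not name arthralgia, while the discontinuation row does, so the difference between routes remains.

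A reader might infer several stronger things that the protocol does not support:

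- *Continuers are never asked.* The adverse-event item is asked of all of them.
- *The module's 'no' and 'unknown' answers cannot be reached.* The header concerns occurrence and the item concerns onset. A woman whose earlier arthralgia persists on treatment can answer 'no', and one with uncertain onset 'unknown'.
- *Every woman who stops is asked directly.* This is not shown for women routed to the Switch module.
- *The missing Arthralgia row in the section 7.2 table proves the gap.* The table has no such row for baseline either, where the module clearly exists.
- *The primary result is biased.* The 14-item VAS score comes from the patient questionnaire, which is used alike for continuers and stoppers.
- *A planned comparison of stoppers with continuers is invalid.* No objective makes that comparison. Compliance is a tablet-intake rating, so any effect on the compliance models is indirect.

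The questionnaire's yes/no question is also a partial safeguard. However, its listed follow-up items give no onset date or relationship to drug, it is mailed with at most one written reminder (section 7.3), and section 11.5 expects 25% to 40% of patient documentation to be inaccessible. The protocol does not say which source counts for incidence.

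**Conclusion.** The point holds in a limited form. Followed as written, the follow-up eCRF ascertains arthralgia differently for women who continue, discontinue or change therapy, and a continuer's blank module is ambiguous. This can under-count arthralgia in continuers and distort those secondary analyses that use eCRF arthralgia, as well as the arthralgia limb of the ITT rule.

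That under-counting does occur, or that arthralgia is falsely tied to stopping, is not established. The size is unknown: the odds ratios of about 2.4 down to 1.1 rest wholly on assumed recording rates and on a rate from much longer follow-up, and they are a yardstick rather than an estimate. All p-values in this study are exploratory (section 11.1), which further limits the consequences. The change is worth making because it is cheap and cannot be made once the data are in.

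**What to change.** Add one mandatory eCRF item at 3, 6 and 9 months for every woman, whether she continues, discontinues or changes therapy: *Arthralgia since the last documentation? no / yes / unknown*, with 'yes' opening the Arthralgia module. Use the same wording in the Treatment discontinuation module.

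Treat a blank as missing, both for incidence and for the ITT rule. This works only together with the mandatory item; alone it would leave mainly women with arthralgia among the continuers who have data. State in section 11.2 or 11.4.1 whether the eCRF or the patient questionnaire is the source for arthralgia incidence.

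The cost is one extra eCRF field per follow-up visit with its branching, and no additional visit or patient questionnaire item.
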